4.2 Exclusion Criteria

In order to qualify for participation, subjects must not meet any of the following criteria:

1	Drug-induced myositis (myositis in patients taking medications known to induce myositis-like syndromes, including, but not limited to, statin agents, fibric acid derivatives, and colchicine).
2	Juvenile polymyositis; inclusion body myositis; cancer-associated myositis, defined as the diagnosis of myositis within 2 years of the diagnosis of cancer except basal or squamous cell skin cancer or carcinoma in situ of the cervix if at least 5 years since excision

3	Myositis in overlap with another connective tissue disease (CTD) that precludes the accurate assessment of a treatment response (for example, difficulty in assessing muscle strength in a scleroderma patient with associated myositis)
4	History of receiving a live vaccine 4 weeks prior to initiation of study treatment
5	Does the patient have any of the following concomitant illnesses that would prevent adequate assessments or in the opinion of the investigator pose an added risk to patient: 
 a. Joint disease, severe calcinosis, or other musculoskeletal condition which precludes the ability to quantitate muscle strength b. Wheelchair bound c. Recurrent or chronic infections, including HIV, hepatitis B or C, TB (incl contact with household contact with active TB and no prophylaxis), or recurrent or active infections with calcinosis d. Symptomatic herpes zoster or herpes simplex (not including just simple oral HSV lesions) within past 12 weeks e. Disseminated/complicated herpes zoster (multi-dermatomal involvement, ophthalmic zoster, CNS involvement, post-herpetic neuralgia f. Known liver disease (i.e. cirrhosis or other conditions compromising the synthetic function of the liver) g. Disorder that would preclude accurate assessment of neuromuscular function? h. Cardiomyopathy or arrhythmias that in the investigators opinion poses an additional risk for study participants. i. New York Heart Association Classification III or IV for congestive heart failure. j. Psychiatric illness that precludes compliance or neuromuscular assessment k. Life threatening non-myositis illness that would interfere with the patient's ability to complete the study l. History of cancer within the last 5 years
6	Known hypersensitivity to abatacept or prior receipt of abatacept
7	Serum creatinine > 2.0mg/dl
8	Pregnant females or nursing mothers
9	Known or suspected history of drug or alcohol abuse within the past 6 months as determined by the medical record or patient interview
10	Anticipated poor compliance
11	Participation in another clinical experimental therapeutic study within 30 days of screening visit.
12	Any history or evidence of severe illness or any other condition that would make the patient, in the opinion of the investigator unsuitable for the study.
13	Low total WBC <2.000, platelets ≤ 100,000/mm ³ ; hemoglobin ≤10 gm/dl

14	History of recurrent infection including active skin infections with calcinosis
15	
Is the patient receiving and concomitant treatment with anti-TNF therapies, rituximab or anakinra or other biologic therapies?
 
Washout period for etanercept is 1 month and anakinra is 1 week Washout period for adalimumab and infliximab is 2 months Washout period for Rituximab is 3 and CD19 has to be detectable and IgG level is within normal limits (normal serum levels of IgG per reference lab: 7-9 years ≥ 572 mg/dl, 10-11 yrs ≥ 698 mg/dl, 12-13 yrs ≥ 759 mg/dl, 14-15 yrs ≥ 716 mg/dl, 16-19 yrs ≥ 549 mg/dl, >19 yrs ≥ 700 mg/dl).

16	Initiation of colchicine and hydroxychloroquine as new drugs during study participation is not allowed.
17	Initiation of statins or fibric acid derivatives during study participation is not allowed.
18	Initiation of an exercise program within 4 weeks of the screening visit. Only a stretching program may be initiated during the study
19	Prisoners or subjects who are involuntarily incarcerated.
20	Subjects who are compulsorily detained for treatment of either a psychiatric or physical (e.g., infectious disease) illness

5.0 CONCOMITANT MEDICATIONS

One of the important issues of trial design involves the use of concomitant medications. IMACS has addressed this by survey and consensus conference format and both adult and pediatric specialists agreed that concomitant corticosteroids should be allowed in a clinical trial, but tapering should follow a standardized reduction regimen. If the patient has achieved the Definition of Improvement (DOI) at week 6 (visit 2) or at any point **thereafter rated moderate improvement compared to the baseline visit and/or mild improvement compared to the last**

visit, tapering of corticosteroids may commence using a dose reduction schedule as follows:

- For patients taking 36 to 60 mg daily, prednisone will be tapered by 10 mg , if they meet the DOI and are rated as at least “at least “mild improvement” compared to the last visit and/or “Moderate improvement” compared to the baseline visit ” by both the physician and the patient or parent (if patient is less than 18 years of age).
- For patients taking 16 to 35 mg daily, prednisone will be tapered by 5 mg , if they meet the DOI and are rated as at least “at least “mild improvement” compared to the last visit and/or “Moderate improvement” compared to the baseline visit ” by both the MD and the patient or parent (if patient is less than 18 years of age).
- For patients taking 6 to 15 mg daily, prednisone will be tapered by 2.5 mg , if they meet the DOI and are rated as at least “at least “mild improvement” compared to the last visit and/or “Moderate improvement” compared to the baseline visit ” by both the MD and the patient or parent (if patient is less than 18 years of age).
- For patients taking 1 to 5 mg daily, prednisone will be tapered by 1 mg if they meet the DOI and are rated as at least “at least “mild improvement” compared to the last visit and/or “Moderate improvement” compared to the baseline visit ” by both the MD and the patient or parent (if patient is less than 18 years of age).
- For patients receiving intravenous pulse methylprednisolone therapy, they may alternatively reduce the dose of IV therapy, instead of oral by a decrease of 25% if they meet the DOI and are rated as at least “at least “mild improvement” compared to the last visit and/or “Moderate improvement” compared to the baseline visit ” by both the MD and the patient or (parent if patient is less than 18 years of age).
- Corticosteroid tapering using the aforementioned guidelines can be commenced at any time on or after week 6 if (a) the patient achieves the DOI and **is rated as at least “mild improvement” compared to the last visit and/or “Moderate improvement” compared to the baseline visit** by both the MD and the patient or parent (for patients less than 18 years of age) or (b) there are complications or circumstances that, in the investigator’s opinion, necessitate the tapering of corticosteroids. The taper schedule is at each visit and the corticosteroid dose will remain stable between study visits. As noted above under Inclusion Criteria #6, it is recommended that patients be on less than 1 mg/kg/day of prednisone at study entry.

Corticosteroid dosing in disease flare:

If in the clinical investigator’s opinion, there are complications or worsening of disease that necessitate an increase in the corticosteroid dose, then the smallest reasonable increase should be considered.

A stable dose of an immunosuppressive (IS) agent must be maintained for a period of 4-6 weeks prior to Visit 1. The dose(s) should be held constant without tapering (unless there is a serious adverse event).

Medications known to induce myositis-like syndromes, including but not limited to, statin agents, fibric acid derivatives, colchicine, and hydroxychloroquine will be subject to the following restrictions. See Tables 1, 2 & 3 below.

5.1 Pre-study drug restrictions

Table 1

Drug	Restrictions
Biologic Agents	See Table Below for washout period.
Prednisone	Stable dose for 4 weeks prior to Visit 1 If discontinued, a washout of 4 weeks is required
IVIG (JDM)	Stable regimen 4 weeks prior to Visit 1. If discontinued a washout period of 8 weeks is required.
IV methylprednisolone (pulse therapy)	Stable regimen 4 weeks prior to Visit 1 If discontinued, a washout of 4 weeks is required
Methotrexate	Stable dose for 6 weeks prior to Visit 1 If discontinued, a washout of 4 weeks is required
Other immunosuppressive agents including: azathioprine, mycophenolate mofetil, leflunomide, cyclophosphamide, tacrolimus or cyclosporine	Stable dose for 6 weeks prior to Visit 1 If discontinued, a washout of 8 weeks is required
Statin agents: Lovastatin, Simvastatin, Pravastatin, Fluvastatin, Atorvastatin and Fibric acid derivatives: Fenofibrate (Lipidil™, Lipidil micro™, Tricor), Gemfibrozil (Lopid™), Benafibrate (Bezalip™), Clofibrate (Atromid-S)	Stable dose for 6 weeks prior to Visit 1
Colchicine	Stable dose for 6 weeks prior to Visit 1
Hydroxychloroquine	Stable dose for 6 weeks prior to Visit 1

	Half-life	Waiting period before enrollment (5 half-lives)	Washout Period
Etanercept	70 hours	15 days	1 month
Adalimumab	14 days	70 days	2 months
Rituximab	32 days	160 days	3 months
Infliximab	9 days	45 days	2 months
Anakinra	6 hours	1 day	1 week

*For rituximab, CD19 has to be detectable and IgG level is within normal limits (normal serum levels of IgG per reference lab: 7-9 years ≥ 572 mg/dl, 10-11 yrs ≥ 698 mg/dl, 12-13 yrs ≥ 759 mg/dl, 14-15 yrs ≥ 716 mg/dl, 16-19 yrs ≥ 549 mg/dl, >19 yrs ≥ 700 mg/dl).

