8	Background therapy with at least 1 non-corticosteroid immunosuppressive agent is required at a stable dose (timeframe mentioned below) prior to the screening visit with the following exception: 
 • There is written documentation in the medical record that the patient is intolerant of an IS agent which is defined as side effects that require discontinuation of the medication(s) or an underlying condition that precludes the further use of the IS medication. Stable dose for 4 weeks: Prednisone, IVIG, IV Methylprednisolone Stable dose for 6 weeks: Methotrexate, Azathioprine, mycophenolate mofetil, leflunomide, cyclophosphamide, tacrolimus or cyclosporine
9	Did an immunosuppressive agent, discontinued prior to the screening visit, have the required washout period: 
 • 4 weeks for prednisone, IV methylprednisolone and methotrexate • 8 weeks for other IS agents including IVIG, Azathioprine, mycophenolate, mofetil, leflunomide, cyclophosphamide, tacrolimus or cyclosporine. • For discontinuation of biologic therapies-with the required washout period

Ve

	Half-life	Waiting period before enrollment (5 half-lives)	Washout Period
Etanercept	70 hours	15 days	1 month
Adalimumab	14 days	70 days	2 months

	washout period for Rituximab is 3 month+ and CD19 has to be detectable and IgG level is within normal limits (normal serum levels of IgG per reference lab: 7-9 years ≥ 572 mg/dl, 10-11 yrs ≥ 698 mg/dl, 12-13 yrs ≥ 759 mg/dl, 14-15 yrs ≥ 716 mg/dl, 16-19 yrs ≥ 549 mg/dl, >19 yrs ≥ 700 mg/dl).
10	If on hydroxychloroquine or colchicine, the dose should be stable for 6 weeks prior to Visit 1
11	Is the statin or fibric acid derivative drug dose stable for 6 weeks prior to the screening visit?
12	Ability of patient or parent to complete self-report questionnaires.
13	If of reproductive potential**, does the patient agree to use a reliable method of birth control during the 24 week duration of the trial and for 100 days after the last dose of study drug was administrated?
14	Does patient agree to forgo immunization with a live vaccine during the course of the study and for at least 3 months after discontinuation of study drug?
15	Patients must have a letter from the referring rheumatologist or specialist supervising the care of the JDM, agreeing to the patient's participation in the study and to continuing to provide care for the patient, including emergency care during the trial.

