7.1. Details on Treatment Schedule and Procedures

A schedule of all study visits and assessments is provided in Appendix E, table 1. Appendix E, Table 2 provides all laboratory studies being performed on screening and throughout the trial. **Patient should be encouraged to adhere to the study visit schedule unless an emergency occurs preventing compliance.**

Screening/enrollment

Subjects will be screened at the screening visit to determine their eligibility for enrollment. The following data are to be collected at Screening Visit for every patient and recorded in the CRF.

- Obtain written informed consent for screening and treatment phase of study, and privacy authorization for release of medical information to include muscle biopsy results and tissue if done previously.
- Demographics: date of birth, sex, race
- Diagnosis of definite or probable JDM by Bohan and Peter criteria (or JDM by newly-developed myositis classification criteria after approval by American College of Rheumatology), and date of diagnosis
- Review inclusion and exclusion criteria for eligibility for study and verify that inclusion/exclusion criteria have been met
- Obtain and record medication history
- Obtain referring physician's contact information, patient release to share information, and agreement with patient's potential entry into trial
- Medical and surgical history: past and current medical and surgical history relevant for purpose of the study.
- Vital signs: height (m), weight (kg), pulse (beats/min), blood pressure (mmHg), and pulse oximetry
- History and physical examination
- Core set measures: CMAS, MMT-8, MDAAT (Extra-muscular Global activity), MD global activity (VAS), MD global damage (VAS), Patient-parent global activity (VAS), CHAQ/HAQ

- Obtain laboratory samples for clinical chemistry (Chem-20, GGT), complete blood count (CBC) with differential, urinalysis, muscle enzymes (CK, LDH, aldolase, AST, ALT), GGT; serologies: HIV antibody, Hepatitis B surface antigen, Hepatitis B core antigen, and hepatitis C antibody, CD19 (for those who received rituximab before) Quantiferon will be completed at the screening visit. If the Quantiferon is indeterminate, then a T spot or PPD will be done.
- Urinalysis
- Collect urine sample for pregnancy for females of child bearing potential (where applicable) Post-menopausal females defined as \geq age 60 and twelve (12) consecutive months of amenorrhea (lack of menstruation) will not be required to undergo pregnancy testing

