- Perform radiographic examination of chest

Some patients may wish to obtain screening labs at home and present the results at the screening visit. This would enable them to enter the intervention phase at the same visit as the screening visit. Results dated within 6 weeks prior to screening visit will be accepted to satisfy eligibility criteria.

All safety labs during the regular study visit may be completed at the home institution up to 10 days prior to the visit and reports sent to GW.

A re-screen protocol will be followed if a period of greater than 45 days elapses between the screening visit and start of treatment.

Visit 1/Week 0 (Intervention phase)

Visit 1(week 0) will occur 0- 45 days after all initial screening evaluations are concluded and the results of screening testing procedures are completed. The subject must remain in the clinic for 15 minutes following administration of study drug. The following evaluations/procedures will be performed at this visit.

- Review of inclusion/exclusion criteria
- NCI Common Toxicity Assessment
- Obtain vital signs (HR,BP,RR, oral temperature and weight, and if indicated, by history of shortness of breath or lung disease, pulse oximetry)
- Medical history and perform a full physical examination
- Collect urine sample for pregnancy test for females of child bearing potential prior to administration of study medication (where applicable)
- Core set activity measures: physician global activity, patient/parent global activity, manual muscle testing (MMT-8), CMAS, HAQ/CHAQ, MDAAT, muscle enzymes, CHQ PF-50/SF- 36, and Disease Activity Score (DAS)
- Myositis Damage Index (MDI): assessment of disease damage completed by the physician during physical examination.
- Physician global damage (VAS)
- Dermatology assessment: CDASI, MD Global Skin Activity + Damage (Optional)
- CDASI, photographs of skin rashes, periungual nailfold capillary assessment.

- Quality of life questionnaires: CHQ PF-50/SF- 36, Dermatology Life Quality Index (DLQI), PROMIS/fatigue, Peds QL fatigue
- Muscle MRI: bilateral thighs and pelvis, axial STIR and T1 images
- Plain radiographs for calcinosis for patients with calcinosis
- Obtain blood samples for Chem-20, GGT, CK, aldolase, LDH, CBC with diff., TSH, anti-thyroid antibodies, von Willebrand Factor antigen level, quantitative immunoglobulins (IgG, IgM, IgA), ANA, ENA, dsDNA, Lymphocyte flow cytometry (TBNK cells)
- Urinalysis

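### Normal IgG is an entry condition after rituximab, but IgG is not among the screening tests and is first drawn at week 0, the visit of the first dose

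*Combined protocol and SAP*

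**What the plan says.** Three places set the same condition for a patient who has had rituximab. The Section 5.1 footnote reads "For rituximab, CD19 has to be detectable and IgG level is within normal limits" and gives lower IgG limits for six age bands. Inclusion criterion 9 (Section 4.1) says "CD19 has to be detectable and IgG level is within normal limits". Exclusion criterion 15 (Section 4.2) says "Washout period for Rituximab is 3 and CD19 has to be detectable and IgG level is within normal limits".

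Under Screening/enrollment, Section 7.1 asks staff to review the criteria and "verify that inclusion/exclusion criteria have been met". The laboratory list there closes with "CD19 (for those who received rituximab before) Quantiferon will be completed at the screening visit" and names no immunoglobulin test. Visit 1 follows 0 to 45 days "after all initial screening evaluations are concluded and the results of screening testing procedures are completed". For laboratory work done at home, Section 7.1 adds: "Results dated within 6 weeks prior to screening visit will be accepted to satisfy eligibility criteria".

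Quantitative immunoglobulins first appear in the Section 7.1 blood list for Visit 1/Week 0. The first injection is on that same visit's list. In Appendix E Table 2, CD19 shares the hepatitis row and is marked for screening. The row for immunoglobulins G and M shows W0 only.

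**The concern.** The entry condition has two parts, and only one has a test at the time eligibility is decided. CD19 was placed at screening expressly for prior rituximab users, so the omission of IgG looks like an oversight. Staff following the visit lists would reach the end of screening with no IgG value to check. They would then draw the first scheduled sample on the day the drug is started.

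Prior rituximab users belong to the intended population: failure of or intolerance to rituximab is one of the refractory-disease items (inclusion 5j). A patient with low IgG after rituximab is someone the protocol means to keep out. If the value is unknown at Visit 1, that safeguard rests on a site noticing the gap. Section 1.3.2 names serious infections among the most serious reactions to abatacept. That low IgG would add to this risk is a clinical assumption, which the documents do not quantify.

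**Working it through.** No design figure is at issue. The check sets the criteria against the schedule, then tests whether the remedy fits the blood-volume limits.

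**1. The two tests side by side (prior rituximab users)**

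| | CD19 detectable | IgG within age limits |
|---|---|---|
| Required by inclusion 9, exclusion 15, 5.1 footnote | yes | yes |
| In the 7.1 screening laboratory list | yes | no |
| Appendix E Table 2 collection time | Screen | W0 |
| First listing in 7.1 | Screening | Visit 1/Week 0 |

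Section 7.1 lists immunoglobulins again at Visit 5, which Table 2 does not. Week 0 is the earliest time in either place. Appendix G names a quantitative immunoglobulin panel without timing.

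**2. Does anything hold the dose for the IgG result?** Visit 1 waits for screening evaluations and the results of screening tests. IgG is not a screening test, so the wait does not reach it. The Visit 1 list opens with a review of the criteria and has the first dose near its end. No line says the IgG drawn that day must be reported first. Laboratory turnaround is not stated.

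**3. Does the remedy fit the pediatric blood limits?** Inputs: Table 2a volumes for children (screening 28.6, W0 105.7, W6 14.6 mL), 2.0 mL for the immunoglobulin row of Table 2, the minimum entry weight of 25 kg, and limits of 5 mL/kg per day and 9.5 mL/kg per eight weeks.

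- Screening draw: 28.6 + 2.0 = 30.6 mL; 30.6 / 25 = 1.2 mL/kg, against 5.
- Screening + W0 + W6: 28.6 + 105.7 + 14.6 + 2.0 = 150.9 mL; 150.9 / 25 = 6.0 mL/kg, against 9.5.

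Screening and week 0 draws are taken to fall on different days, because Visit 1 needs the screening results and same-day entry relies on laboratory work already done at home.

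**4. Does Table 2a conceal a screening IgG?** Blood rows marked for screening in Table 2:

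- Children: 2.5 + 1.5 + 0.6 + 5.0 + 3.0 + 1.0 + 2.0 + 8.0 + 3.0 = 26.6 mL, against 28.6 in Table 2a.
- Adults: 4.0 + 3.0 + 0.6 + 5.0 + 3.0 + 1.0 + 2.0 + 12.0 + 3.0 = 33.6 mL, against 35.6.

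Both totals exceed the rows by 2.0 mL. From week 6 onward, Table 2a agrees with the blood rows within 0.1 mL. Week 0 does not reconcile: 99.6 against 105.7 mL (children) and 102.6 against 114.2 mL (adults).

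**The case against.** The strongest reply is that the protocol already forbids what is feared. Section 4.1 makes every criterion mandatory. Inclusion 9 prints the IgG limits inside the eligibility checklist, so staff cannot properly complete that item for a prior rituximab user without a value. The criteria are checked at screening and again at Visit 1, and only eligible subjects start drug. This stands. A reader might infer that the protocol permits dosing before eligibility is known. It does not: dosing without an IgG value would be a breach. What survives is narrower: the schedule does not produce the value that the criterion needs.

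Second, a route to a value exists. Outside results up to 6 weeks old are accepted, and safety laboratory work for regular visits may be done at home up to 10 days earlier. A careful site could use either, or wait for the week 0 result. But both provisions are permissive and neither names IgG. The Visit 1 blood list also lacks the home-institution note that Visits 2 to 5 carry.

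Third, the extra 2.0 mL in the Table 2a screening totals equals the immunoglobulin tube, so the W0 entry in Table 2 could be a labelling slip. That remains possible, but the lymphocyte phenotyping and ANA/ENA tubes are also 2.0 mL, and the week 0 totals do not reconcile either. The surplus does not establish a screening IgG, and the Section 7.1 list would still omit it.

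**Conclusion.** The point holds as a mistimed eligibility test. The criteria require a normal IgG after rituximab and Section 7.1 requires verification at screening, yet both schedules first supply IgG at the visit of the first dose, outside the wait for screening results. Severity is minor; this is a cheap improvement in patient safety.

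Its reach is limited to prior rituximab users. The documents do not say how many to expect, and there may be none. The timing consequence also assumes that the site has no recent outside value and that the laboratory does not report before the injection.

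Two larger conclusions are not supported. A reader might infer a bias in the week-24 improvement rate, since a patient found ineligible after dosing would remain in the intention-to-treat analysis of Section 15.0. Nothing in the documents shows that a low-IgG patient would respond differently, so no effect on the endpoint is claimed. A reader might also take the serious-infection rates in Section 1.3.2 (3.0% on abatacept, 1.9% on placebo) as the size of the hazard. Those come from intravenous treatment in adult rheumatoid arthritis and are not broken down by IgG.

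**What to change.** 1. In the Section 7.1 screening list and Appendix E Table 2, add quantitative IgG at screening for patients who have received rituximab, beside CD19. An outside result within the existing 6-week window may serve.
2. Under Visit 1 in Section 7.1, state that for these patients the CD19 and IgG results must be on file and within limits before the first dose.

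The cost is one assay, at most 2 mL on a draw already planned, for prior rituximab users only. If the Table 2a screening total already allows for the tube, the planned volume does not change. A patient who arrives without an IgG result could lose same-day entry and have to return for Visit 1.
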